In this study, we use the blood vessels in the skin as a representative vascular bed for examining mechanisms of microvascular dysfunction in humans. Using a minimally invasive technique (intradermal microdialysis for the local delivery of pharmaceutical agents) we examine the blood vessels in a dime-sized area of the skin in healthy young women and men. As a compliment to these measurements, we also draw blood from the subjects and measure circulating factors that may contribute to cardiovascular health.

I.5 *Specify your research question(s), study aims or hypotheses (do not indicate "see protocol")*
The aim of this proposal is to define the mechanistic role of activation of AT2Rs in young men and young women. To accomplish this aim, we will test the following hypotheses:

Hypothesis 1: AT2R activation (C21) will have greater microvascular dilation in young women vs young men.
Hypothesis 2: The dilatory response to C21 will be enhanced in both young women and men with AT1R inhibition (losartan) vs control.

I.6 *Background and significance and/or Preliminary studies related to this project.
(do not indicate "see protocol")*

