needle and then withdraw the needle leaving the tubing in the skin. Any hyperemia related to the insertion subsides in about 60 minutes. When the hyperemia induced by inserting the tubing in the skin subsides, the experiment begins. During this time Lactated Ringer's perfuses the tubing. The researchers tape a fiber optic laser Doppler flowmeter probe and its holder over each microdialysis site. The researchers control the temperature of the holders. The holders start at 33°C (91.4°F). During the experiment, the computerized data acquisition system records heart rate, skin blood flow, and skin temperatures continuously. The researcher and/or an automated critical care monitor measures blood pressure at 5-7 minute intervals.

Local Heating Protocol: The intradermal microdialysis probes are randomly numbered 1 or 2 and assigned to receive doses of Lactated Ringer's (probe 1) or Losartan (probe 2).

Probe 1. Lactated Ringer's only

Probe 2. Lactated Ringer's + Losartan

Initially, Lactated Ringer's flows through all probes. Then the investigational agents are added to the Lactated Ringer's flowing through MD probe 2 for 60 minutes. When the skin blood flow is stable, we perform a 20-minute baseline and set of measurements, including placement of 3 ECG electrodes for the collection of heart rate. After we have collected baseline data, we begin the dose-response protocol. We add identical concentrations of C21 to the perfusate in probes 1 and 2. At 10-minute intervals, we increase the concentration of C21 in the perfusates in identical fashion in probes 1 and 2. The participant receives 10 different concentrations of C21. After perfusing the last concentrations, all MD sites are then warmed to 43°C (108°F) to perform Maximal Skin Blood Flow. At the same time, the researchers switch the fluids at all sites to Ringer's + SNP for about 30 minutes. This causes the blood vessels at the MD sites to dilate or enlarge as much as they can. The researchers then de-instrument the subject, remove the microdialysis fibers, and apply sterile dressings. The subject is given verbal and written instructions for how to care for the microdialysis sites. The researcher measures final vitals before the subject departs.

VII.E.7 *Will you attempt to recontact subjects who are lost to follow-up?*
No - followup is not required in this study

VII.E.9 *Will subjects be provided any compensation for participating in this study?*
Yes

VII.E.10 *Cash*
No

VII.E.11 *Gift Card*
No

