No

XI. Data Analysis

XI.1

Describe the analysis methods you will use, including, if applicable, the variables you will analyze

The primary outcome variable will be cutaneous vascular conductance, which is calculated from laser-Doppler flux/mean arterial pressure. Three-way repeated measures ANOVA (group, MD site, dose) will be used to examine group differences and local microdialysis treatment differences across the doses of pharmacological stimuli. Appropriate post-hoc analyses with corrections for multiple comparisons will be performed when main effects are identified, including potential confounding variables as covariates. Paired t-tests will be used to examine group differences in subject characteristics.

XI.2

Provide the rationale or power analysis to support the number of subjects proposed to complete this study.

Using previously published data that determined differences in cutaneous vascular conductance (CVC), an index of skin blood vessel dilation, the results of a power analysis indicated that 24 young men and women (12 subjects x 2 groups) will be sufficient to detect a meaningful physiological difference (power=0.80, $\alpha=0.05$) of a ~10% change in CVC from baseline between microdialysis treatment sites and sex differences (men and women). Based on the available literature and on prior experience with microdialysis studies, the standard deviation of the difference is ~10%. After accounting for attrition, withdrawals, and screen failures, we conservatively estimate that 44 people will need to be consented and screened in order to arrive at this target number of 24.

XII. Future Research

XII.1

Do you wish to keep any information about subjects involved with this research project so that members of the current research team may contact them in the future for your own research projects?

Yes

XII.2

Do you wish to keep any information about subjects involved with this research project so that [other researchers](#) may contact them for future research?

No

XII.3

List the data or information you will keep:

Name

Race/ethnicity

Birthdate

Sex

Contact information (mailing address, e-mail address, phone number)

XII.4

Does this project involve storing any data, tissues or specimens for future research?

Yes – contribution for future use is optional

XII.5

Describe how you will keep track of those who consent to future use and those who do not and how you will prevent future use for those who do not consent.

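### XI.2's power of 0.80 at an unadjusted alpha of 0.05 makes no allowance for XI.1's corrected tests over 10 concentrations, and can overstate power for the sex contrast and for losartan within each sex

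*Combined protocol and SAP*

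**What the plan says.** Section I.5 sets two hypotheses. The first is that "AT2R activation (C21) will have greater microvascular dilation in young women vs young men". The second is that "The dilatory response to C21 will be enhanced in both young women and men with AT1R inhibition (losartan) vs control".

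Section VII.E.6 describes two microdialysis sites per participant (Ringer's alone, and Ringer's with losartan), with C21 raised stepwise at both: "The participant receives 10 different concentrations of C21".

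Section XI.1 makes CVC the primary outcome and plans a three-way repeated measures ANOVA on group, site and dose. It then states: "Appropriate post-hoc analyses with corrections for multiple comparisons will be performed when main effects are identified". It names neither the correction nor the family of comparisons, and it ties neither hypothesis to a concentration, a dose-response summary or a term of the model.

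Section XI.2 states that "the results of a power analysis indicated that 24 young men and women (12 subjects x 2 groups) will be sufficient to detect" a difference of about 10% in CVC change from baseline, with "power=0.80, $\alpha=0.05". The one figure covers the site contrast and the sex contrast together. The only variability given is that "the standard deviation of the difference is ~10" per cent. The test, its sidedness, the concentration and any multiplicity allowance are not stated.

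**The concern.** The power statement describes a single comparison at alpha 0.05. The analysis section contains no such comparison: it has a factorial ANOVA over 10 concentrations, then follow-up tests at a stricter level. The 0.80 is therefore not a property of the analysis that will be run.

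Hypothesis 1 is the study's title question, and it rests on a between-person contrast of 12 against 12. A null result would be read as coming from a trial with 80% power when the chance of detecting the stated difference might have been much lower. A positive result has the opposite weakness. With no concentration or summary fixed in advance, it could come from any of the 10 concentrations or from a model term, and the plan does not say which of these would count as support for the hypothesis.

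**Working it through.** **Inputs from the documents.** True difference 10%, SD of the difference 10%, 12 completers per sex (24 in all), alpha 0.05, power 0.80 (all XI.2); 10 concentrations (VII.E.6); corrected post-hocs (XI.1).

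**Assumptions.** Tests are two-sided. XI.2 gives no between-person SD, so I use 10% and, as a favourable alternative, 10/√2 = 7.07%. Correction is Bonferroni over m comparisons, alpha = 0.05/m; m = 10 is one comparison per concentration.

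**Formulas.** Power is from the noncentral t distribution.
- Unpaired, n per group: noncentrality = (difference/SD) × √(n/2), df = 2n − 2. For 12 vs 12 at SD 10%: 1 × √6 = 2.449, df 22, critical t 2.074 at alpha 0.05 and 3.119 at 0.005.
- Paired, n people: noncentrality = (difference/SD of difference) × √n, df = n − 1. For n = 12: √12 = 3.464, df 11, critical t 2.201 and 3.497. For n = 24: √24 = 4.899, df 23, critical t 2.069 and 3.104.

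**Step 1: the plan's own figure.** At alpha 0.05, 12 vs 12 gives 0.65 (0.69 by the normal approximation), and 17 per group would be needed for 0.80. Paired, n = 12 gives 0.88 and n = 24 gives 0.997. One-sided, 12 vs 12 gives 0.77 (0.79 by the normal approximation). That last variant is close to 0.80, but it uses a one-sided alpha and treats an SD of the difference as a between-person SD, neither of which is stated, and it does not give 0.80 for the site contrast. No single variant gives 0.80 for both contrasts.

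**Step 2: corrected tests at one concentration.**

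| Contrast, true difference 10% | Uncorrected | m = 2 | m = 5 | m = 10 |
|---|---|---|---|---|
| Women vs men, SD 10% | 0.65 | 0.53 | 0.38 | 0.28 |
| Women vs men, SD 7.07% | 0.91 | 0.85 | 0.73 | 0.64 |
| Losartan vs control, one sex (n = 12) | 0.88 | 0.79 | 0.64 | 0.52 |
| Losartan vs control, shown in both sexes | 0.78 | 0.63 | 0.41 | 0.27 |
| Losartan vs control, pooled (n = 24) | 0.997 | 0.99 | 0.98 | 0.95 |

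The fourth row is the square of the third before rounding, since the sexes are independent samples: 0.883² = 0.78 and 0.518² = 0.27. The pooled contrast still has 0.87 with 40 comparisons.

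**Step 3: the sex main effect.** The ANOVA averages over concentrations. With SD 10% at each and a common correlation ρ between them, the SD of a 10-concentration mean at one site is 10 × √((1 + 9ρ)/10): 7.42 at ρ = 0.5 and 9.54 at ρ = 0.9. If each site has SD 10% and the difference has SD 10%, then 2 × 100 × (1 − r) = 100, so the between-site correlation is r = 0.5 and averaging both sites multiplies the SD by √0.75.
- Uniform 10% effect: 10/7.42 = 1.35 gives 0.88, and 10/9.54 = 1.05 gives 0.69. Averaged over both sites: 0.95 and 0.81.
- Effect rising from 1% to 10%, mean (1 + … + 10)/10 = 5.5: 5.5/7.42 = 0.74 gives 0.41, and 5.5/9.54 = 0.58 gives 0.27. Averaged over both sites: 0.52 and 0.34.

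So the main effect has 0.69–0.95 under a uniform effect and 0.27–0.52 under a rising one. The documents give neither the dose profile nor ρ.

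**The case against.** A reader might infer that no route in XI.1 reaches 0.80. The documents do not support that. The pooled site contrast keeps 0.95 after a 10-fold correction, and the sex main effect can exceed 0.80 if the effect is uniform over concentrations.

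A reader might also infer that the main effect is diluted by inactive doses. Section VII.E.6 gives rising concentrations and no expected effect at any of them, so the dose profile is an assumption. Averaging also reduces variance, so the result can go either way.

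The group by dose interaction is a further route, since a sex difference that grows with concentration appears there. Under the 1% to 10% rise at one site, simulation gives 0.81 with equal correlation 0.7 (about 0.72 with a Greenhouse-Geisser correction), but 0.28–0.41 with serial correlation 0.8–0.9 and that correction. This route again depends on quantities that are not stated.

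The family of 10 is an assumption too, and milder corrections exist. Holm gives 0.29–0.37 per concentration for the sex contrast. Counting success at any active concentration (3 to 10 active, correlation 0.5–0.8) gives 0.43–0.76 for sex, and 0.69–0.95 for losartan within one sex. That rule helps, but the sex figures stay below 0.80 at SD 10%, and XI.1 does not adopt it.

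Nor is multiplicity the only cause. At SD 10% the sex contrast has 0.65 before any correction, because an SD of a difference is being used for an unpaired contrast. With SD 7.07% it has 0.91 uncorrected and still 0.85 with 2 comparisons.

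Finally, Hypothesis 2 could be read as the pooled site effect, which is well powered. But a pooled effect does not by itself show enhancement in both sexes. Section VII.B.11 mentions a separate written protocol, which may say more; if so, section XI should agree with it.

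These objections narrow the claim. They leave standing that the stated power is for a test the analysis section does not contain.

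**Conclusion.** The point holds in a limited form. XI.2 states 0.80 at an unadjusted 0.05 for both contrasts and allows nothing for the corrections that XI.1 commits to. For a test at one concentration with a 10-fold correction, power for Hypothesis 1 is 0.28 (0.64 at the favourable SD). For Hypothesis 2 it is 0.52 within one sex and 0.27 for both. The pooled losartan contrast is unaffected. Power for the sex main effect runs from about 0.27 to 0.95 over the profiles and correlations tried.

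The figures rest on a two-sided test, the plan's 10% difference, an assumed between-person SD and an assumed family of comparisons. The mismatch between XI.1 and XI.2 does not depend on those choices; its size does. That width is itself a reason to fix the test in advance, because the plan leaves open which of these powers applies.

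**What to change.** In XI.1, name one CVC summary per participant per site, chosen before data are seen: for example, the area under the dose-response curve, or the mean change from baseline over a pre-set range of concentrations. Set one contrast per hypothesis at alpha 0.05: women versus men at the Ringer's site for Hypothesis 1, and losartan minus control within each sex for Hypothesis 2. Keep the three-way ANOVA and the corrected per-concentration tests as supportive, and name the correction and its family.

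In XI.2, restate power for each contrast separately. Give a between-person SD and its source for the sex contrast, and give the power for success in both sexes for Hypothesis 2.

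The change needs no further participants or measurements. Its costs are a less favourable stated power and the demotion of per-concentration results. It defines the test and corrects the figure, but it does not by itself restore 0.80 for the sex contrast: that stays near 0.65 at SD 10%, where 17 per sex would be needed. The sponsor would then either justify a smaller between-person SD, revisit the number, or state the lower power openly.

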V.21 *Will any portion of this project be conducted in the CRU, or does it use any CRU resources?*
No

V.22 *Will this project use:*

- *any resource/patients of the Holden Comprehensive Cancer Center*
- *involve treatment, detection, supportive care, or prevention of cancer*

No

V.25.a *Will the study involve any of the following activity at UI Health Care, even if subjects or their insurance will not be billed for the item or service, and regardless of the study funding source (including studies with departmental or no funding)?*

- *Procedures, tests, examinations, hospitalizations, use of Pathology services, use of clinic facilities or clinical equipment, or any patient care services, including services conducted in the Clinical Research Unit; or*
- *Physician services or services provided by non-physicians who are credentialed to bill (ARNPs, Physician Assistants, etc.)*

No

V.26 *The study involves Department of Nursing Services and Patient Care nursing, nursing resources or evaluates nursing practices at UI Health Care.*
No

V.27 *Will the study involve the use of the I-CTMS (OnCore) for clinical trial data management? Select yes if any or all of the following apply:*

- *Any study required to register subjects in EPIC are encouraged to use the I-CTMS*
- *Best practice is to use the I-CTMS for any new study that involves subject tracking or sponsor invoicing*

Note: This question is for non-oncology studies only. For oncology studies use existing HCCC OnCore processes by selecting V.22
Yes

V.28 *Identify the role of each research team member.*

Name	Role

Name	Role

VI. Subjects

VI.1 *How many adult subjects do you expect to consent or enroll for this project?*
44

VI.2 *What is the age of the youngest adult subject?*
18.0

VI.3 *What is the age of the oldest adult subject?*
35.0

VI.4 *What is the percentage of adult male subjects?*
50

VI.5 *What is the percentage of adult female subjects?*
50

VI.6 *How many minor subjects do you expect to consent or enroll for this project?*
0

VI.13 *Describe EACH of your subject populations*

- *Include description of any control group(s)*
- *Specify the Inclusion/Exclusion criteria for EACH group*

In this study we are recruiting 2 subject groups. This will include 1) young women and, 2) young men. Participants must be 18-35 years old with a body mass index between 18 and 30 kg/m², a systolic blood pressure <140, and diastolic blood pressure <90 mmHg.

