- **Registry** – The collection and maintenance of data (not including biologic samples) in which: (1) the individuals in the registry have a common or related condition(s), and/or (2) the individuals in the registry are interested in being contacted for future studies by investigators other than those listed in Section II of this project. ([UI Guide](#))
- **Repository** – The collection, storage, and distribution of human biologic samples and/or data materials for research purposes. Repository activities involve three components: (i) the collection of data and/or specimens such as blood, tissue, saliva, etc.; (ii) the storage of data or specimens, and data management function; and (iii) the sharing of data/specimens with recipient investigators other than the original investigators. (paraphrased from [OHRP](#))
- **Other**

VII.B.2 *Does this project involve a drug washout (asking subject to stop taking any drugs s/he is currently taking)?*

No

VII.B.11 *Is there a separate, written protocol that will be submitted in addition to this IRB New Project form? (Note: a grant application is not considered to be a protocol)*
Yes

VII.B.12 *Who initiated/provided the protocol?*
UI Investigator

VII.B.12.c *Would you like to use information from this IRB application to have a ClinicalTrials.gov record started on your behalf?*
No

VII.B.14 *Protocol#:*
202206519

VII.B.15 *Protocol Version#:*
1

VII.B.16 *Protocol Date:*
7/13/2022

VII.B.17 *Amendments submitted with this application:*
Amend. # **Amend. Date**
Nothing found to display.

VII.B.18 *Does this project involve the evaluation, or testing, of the safety and/or efficacy of a medical device?*
No

VII.C. Project Description (C)

VII.C.1 *Does this project involve any [research on genes or genetic testing/research](#)?*
No

VII.D. Project Description (D)

VII.D.1 *Check all materials/methods that will be used in recruiting subjects (you will need to attach copies of all materials at the end of the application):*

- Advertisements -
- Posters -
- E-mail -
- Website - UIHC Clinical Trials and Research Website <https://microvascularphys.lab.uiowa.edu/research-studies>

VII.D.1.a *Will any of the materials/methods below be used by researchers (or their colleagues) to recruit subjects into this study?*

- *the potential subject is a patient OR*
- *use of any information considered to be Protected Health Information (PHI) OR*
- *review of patient/clinic records be used in recruiting subjects*

No

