- *Include when recruitment and consent materials are used*
- *Use 3rd person active voice "The Principal Investigator will identify subjects. For example, the principal investigator will identify potential subjects, the study coordinator will discuss the study with subjects over the telephone and schedule the first study visit, etc..."*
- *Describe the steps that will be taken by the research team to minimize the possibility of coercion or undue influence during the consent process*

The subjects will consist of young, healthy men and women between the ages of 18-35 years of age. The PI and research staff will recruit subjects from Johnson county and surrounding areas via flyers, table tents, digital signage, emails, The UI mass-email system, newspaper and newswire ads, and posting on the UIHC website for research volunteers. The UIHC Clinical Trials and Research Website will have this research study available as

a listed research study for potential research subjects to find out more information and express interest in participating. Subjects will be asked to contact the research staff via phone or email. Based on how the subject reached out, a study team member will then either 1) contact the potential participant by phone (see pre-consent phone script) or 2) email the participant back with study information (see email correspondence to recruit subjects). If the potential subject is still interested, they will be sent a link to the pre-consent screening survey (see pre-screening survey). If the potential subject DOES NOT qualify based on the pre-screening survey, researchers will notify them and list a reason for ineligibility. If the subject DOES qualify, researchers will reach out by phone or email to schedule visit 1. Subjects will be sent the consent summary by e-mail before visit 1. Visit 1 will include a detailed description of the study and review of the informed consent, including risks. If subjects are not able to understand the protocol and instructions for any reason, written or verbal, they are not included in the study. Subjects are informed throughout the consenting, screening, and conduction of the study that they may discontinue their participation at any time with no penalty to them. If the subject signs the informed consent, they are given a copy of the signed document to take home with them.

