VII.D.37 *Does the study include any form of deception (e.g., providing participants with false information, misleading information, or withholding information about certain study procedures)?*

Examples:

- *Procedure includes a cover story that provides a plausible but inaccurate account of the purposes of the research.*
- *Participants will be provided with false information regarding the particular behaviors of interest in the research.*
- *Procedures include a confederate pretending to be another participant in the study.*
- *Participants will be told that the research includes completion of a particular task, when in fact, that task will not be administered.*
- *Study is designed to introduce a new procedure (or task) that participants are not initially told about.*
- *If yes, a waiver of informed consent must be requested under question IV.3.*

No

VII.E. Project Description (E)

VII.E.1 *Will subjects be randomized?*

No

VII.E.3 *Will any questionnaires, surveys, or written assessments be used to obtain data directly from subjects in this study?*

Yes

VII.E.4 *List all questionnaires, surveys, written assessments and ATTACH each one to the application. (NOTE: You are NOT prohibited from attaching copyrighted materials to this application)*
Participant information survey
Health history questionnaire

VII.E.5 *Does this project involve creating any audiotapes, videotapes, or photographs?*

No

VII.E.6 *Provide a detailed description in sequential order of the study procedures following the consent process - DO NOT cut and paste from the Consent Document.*

Describe study populations separately if they will be participating in different procedures - include CONTROL population if applicable.

DESCRIBE:

- *What subjects will be asked to do/what happens in the study (in sequential order)*
- *The time period over which procedures will occur*
- *The time commitment for the subject for individual visits/procedures*
- *Long-term followup and how it occurs*

Visit 1 - Consent and Screening (approximately 1 hour)

The PI or research staff explain the study and go over the informed consent with the participant. After the participant signs the informed consent, the PI or research staff performs the physical screening that includes urine pregnancy test for women, heart rate (HR), blood pressure (BP), height, and weight measurements. The participant fills out the health history questionnaire and participant info survey.

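### Paired t-tests are named for comparing the characteristics of women and men, who are independent groups with no matching described

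*Combined protocol and SAP*

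**What the plan says.** Section XI.1 gives one sentence on subject characteristics: "Paired t-tests will be used to examine group differences in subject characteristics".

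The rest of the document fixes what a group is:

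- Section VI.13 defines the populations: "In this study we are recruiting 2 subject groups. This will include 1) young women and, 2) young men". VI.4 and VI.5 put each sex at 50%.
- XI.1 gives the main analysis: "Three-way repeated measures ANOVA (group, MD site, dose) will be used to examine group differences". Group is listed there as a factor distinct from microdialysis site and dose.
- XI.2 sizes the study by group: "24 young men and women (12 subjects x 2 groups) will be sufficient".
- VII.D.29 describes enrollment for both sexes together: "The subjects will consist of young, healthy men and women between the ages of 18-35 years of age".
- VII.E.6 lists the Visit 1 measurements, including "heart rate (HR), blood pressure (BP), height, and weight measurements".

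The plan does not define which variables count as subject characteristics.

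**The concern.** A paired t-test analyses differences within pairs, so each observation in one group needs a specific partner in the other. That holds for two measurements on one person, or for individually matched people. Neither is described for the comparison of women with men.

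An analyst who followed the sentence literally would have to make up the pairing, most likely from the order of rows in the data file. The result would then depend on something with no scientific meaning. It would also use half the degrees of freedom and could not use everyone if the group sizes differed.

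At stake is the table showing how the two sexes compare. Because VII.E.1 says subjects are not randomized, readers will rely on that table to judge comparability.

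**Working it through.** **Step 1: is there any pairing in the design?**

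- *Within a person.* The only paired structure is the two microdialysis probes in each participant (VII.E.6). Characteristics such as height and weight do not vary by probe. Heart rate and blood pressure are recorded at Visit 1 and again at Visit 2, but repeated readings on one person do not pair a man with a woman.
- *Between persons.* VI.13 sets common limits for age, body mass index and blood pressure. VII.D.29 describes recruitment and consent. Neither contains a matching rule. The term age-matched occurs only in background text on cardiovascular risk (I.4, I.6, IX.2).
- *Meaning of group.* XI.1 separates group from site and dose, and XI.2 multiplies subjects by groups. Group therefore means sex.

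So no pairs are defined.

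**Step 2: cost at the planned size.** The plan attaches no figure to this comparison, so there is none to reproduce. Inputs: n = 12 per group (XI.2). Assumptions: two-sided test at 0.05, normal data, equal SDs, true difference of d SDs, and pairing unrelated to the values.

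- Independent test: df = 2n − 2 = 22, critical t = 2.074, noncentrality d·√(n/2) = d·√6 = 2.449 at d = 1.
- Paired test on arbitrary pairs: df = n − 1 = 11, critical t = 2.201. The SD of a difference between unrelated people is √2 SD, so the noncentrality is (d/√2)·√12 = d·√6, the same value.

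The power loss thus comes only from the lost degrees of freedom:

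| True difference | Independent | Paired, arbitrary |
|---|---|---|
| 0.8 SD | 0.466 | 0.432 |
| 1.0 SD | 0.649 | 0.608 |

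**Step 3: unequal completion.** The plan gives no split other than 12/12; those below are assumed, with 24 completers and d = 1. The independent test has noncentrality √(n₁n₂/24) and 22 df. The paired test has m pairs, where m is the smaller group, with noncentrality √(m/2) and m − 1 df.

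| Split | Dropped by pairing | Independent | Paired |
|---|---|---|---|
| 13/11 | 2 | 0.646 | 0.563 |
| 14/10 | 4 | 0.636 | 0.514 |
| 15/9 | 6 | 0.621 | 0.463 |

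**Step 4: error rate and dependence on the pairing.** In 200,000 simulated data sets of 12 versus 12:

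- With no true difference, type I error was 0.0498 paired and 0.0495 independent, so it is not inflated.
- The two tests gave different verdicts at 0.05 in 2.7% of data sets with no true difference and 9.8% with a 1-SD difference.

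As an illustration, one simulated data set with an observed difference of 0.85 SD had an independent-test p of 0.049. Re-pairing the same 24 values at random moved the paired p from about 0.008 to 0.126 (central 95% of orderings), and it fell below 0.05 in 37% of them.

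**The case against.** The strongest reply is that this is a slip for unpaired. The same section treats sex as a between-subject factor and the sentence itself speaks of group differences, so the intended comparison is clear. The harm then arises only if someone follows the word literally, and the plan nowhere describes a row-order pairing. That is a fair reading and supports a low severity. It does not remove the point, because no other text corrects the word. X.4 says data will be entered into SPSS, where the paired and independent tests are separate procedures.

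Second, matching might be described elsewhere. VII.B.11 asks "Is there a separate, written protocol that will be submitted in addition to this IRB New Project form" and the answer is yes. That protocol is not available here, so matching cannot be ruled out. XI.1 would still need a sentence saying what is paired.

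Third, the larger power losses rest on splits that depart from the planned 12/12. This stands: at the planned size the loss at 1 SD is only 0.649 − 0.608 = 0.041. Unequal completion is plausible, since XI.2 allows for attrition and withdrawals, but its extent is unknown.

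Fourth, the figures are for the pooled-variance test, whereas Welch is offered as an example of the fix. With equal SDs and equal group sizes the difference is trivial, and either independent test would resolve the point.

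**Conclusion.** The concern holds. On the design described, the paired t-test is the wrong test for comparing women with men.

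The consequence is minor: at 12 per group, about 0.04 of power at 1 SD, no inflation of type I error, p-values that depend on an arbitrary pairing, and subjects lost if the groups end up unequal. The three-way ANOVA of cutaneous vascular conductance and both hypotheses are unaffected. XI.1 mentions confounders as covariates but does not say these tests choose them, so no effect by that route is claimed.

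The power and simulation figures rest on assumed normality, equal SDs and standardised differences, because the plan gives no SDs for subject characteristics. The conclusion about the test does not depend on them. It does depend on there being no individual matching in the separate protocol.

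**What to change.** In XI.1, replace the paired t-tests with independent-samples (unpaired, for example Welch) t-tests for subject characteristics in women versus men. If individual matching is in fact used, keep the paired test and add a sentence giving the matching variables and how pairs are formed.

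The cost is a word or two, or one sentence. Data collection, sample size and the primary analysis do not change.
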